2.7. Studies and considerations on safety related to the medicinal product

2.7.1. Biodistribution and vector shedding

It is expected that the biodistribution of the autologous transduced CD34+ cells reflects that of untransduced HSPC, which migrate to the lympho-hematopoietic organs of conditioned transplant recipients. In addition, the hematopoietic progeny of the engrafted HSC will also infiltrate non-hematopoietic tissues to become resident or migrating extra-vascular hematopoietic lineage cells. Biodistribution studies were performed in RAG2^{-/-}IL-2ryc^{-/-} neonate mice, which represent a suitable model to study engraftment and differentiation of human HSPC ([Traggiai Chicha et al. 2004](#)). Human derived umbilical cord blood (UCB) CD34+ cells were transduced with clinical grade vector according to the manufacturing procedure established for the clinical

trial. The transduction efficiency was on average 72% as assessed in a CFU-C assay and the mean integrated VCN on cultured cells was 1.5. After transduction, 0.3×10^6 human CD34+ UCB cells were transplanted into each RAG2-/-IL2r- γ c-/- neonate mouse. This dose corresponds to 1×10^8 CD34+ cells/kg, thus largely exceeds the 5×10^6 /kg average dose that will be administered to patients. Control animals were transplanted with untransduced (UT) or unmanipulated (UM) UCB cells, transplanted in equal doses. Mice were euthanized 2 months post-infusion and their lympho-hematopoietic organs (BM, liver, spleen, thymus) were collected for further studies. In addition, brains and gonads (as representative non-hematopoietic organs) were collected from male mice after perfusion with saline solution.

We found no differences in the biodistribution of the UT, UM and transduced human UCB cells, including CD34+ cells in the BM. A normal differentiation pattern into T cells was observed in the thymus and differentiated B cells were normally represented in the BM and spleen of mice treated with transduced human HSPC. qPCR (quantitative polymerase chain reaction) documented the presence of LV in hematopoietic organs of all mice transplanted with transduced CD34+ cells. The results obtained from both brain and gonads for LV and human genome sequences were below the sensitivity threshold of the assay (< 16 copies in 10^5 cells).

Upon transduction, the vector becomes stably integrated as a provirus within the chromatin of target cells. Because of the replication-defective nature of the vector, there is no possibility of spontaneous mobilization of the provirus from the transduced cells unless helper functions are also provided in the transduced cells either by recombination during vector production or by super-infection with wild-type HIV in an infected host. Both of these possibilities are extremely unlikely, because: 1) the multi-split design of the packaging system and the lack of homology between the envelope and transfer vector genome make extremely unlikely that a replication-competent recombinant be generated during production; 2) the self-inactivating feature of the vector LTR prevents transcription from the proviral LTR and thus prevents vector mobilization even in the case of recombination with the packaging constructs or superinfection of the transduced cell by wild-type HIV-1, as we have previously reported ([Bukovsky et al. 1999](#)). There is however the concern that some infectious vector particles remain associated with the transduced cells and that can be subsequently released to transduce bystander cells as shown with our laboratory-grade vector stocks in CD34+ cells cultured with stromal cells and other Authors using mouse HSPC ([Pan et al. 2007](#)). Whereas the amount of vector being released is conceivably limited and thus the chance of off-target transduction is low, the potential release of some infectious vector from the transduced cells after *in vivo* infusion may raise concerns on its biodistribution and the potential transduction of unwanted cell types which are typically associated with *in vivo* vector administration. We have set up experiments specifically aimed at assessing the extent of vector release from previously transduced human HPSC. Our results show that: 1) vector release and bystander transduction can occur but at substantially lower level when using vector stocks from the large-scale production and purification process used for GMP production, as compared to laboratory grade stocks. This difference may be due to the fact that the latter are concentrated by ultracentrifugation without further purification and may contain larger amount of impurity and aggregated particles; 2) exposure of the transduced HSPC to autologous human plasma significantly inhibits bystander transduction, so that it becomes virtually undetectable when using large scale LV stocks. These findings suggest that in the clinical setting, in which the transduced cells are inoculated into the bloodstream of human

patients, the potential occurrence of bystander cell transduction may be reduced to negligible levels.

Moreover, to directly assess the eventual occurrence of bystander cell transduction upon *in vivo* infusion of transduced cells, we have exploited the vector integration studies performed in the organs of *Rag2*-, *Il2r-gamma chain*-/- mice transplanted with transduced HSPC. DNA extracted from the organs of the transplanted mice was analyzed for the content of vector DNA and human genome by qPCR as described above. In the experiment performed we have observed corresponding estimates for: 1) the extent of human cell repopulation estimated by FACS analysis for cells expressing the human hematopoietic marker CD45 and the proportion of human genome over mouse genome in the total DNA extracted from the organ (as estimated by qPCR for human telomerase and mouse b-actin); 2) the vector content *per* human genome in the different organs (as estimated by qPCR for vector sequence versus human telomerase). The results obtained with this strategy, indicate that in the mouse organs tested the vector distributes together with the human cells and that at least the vast majority of the detectable vector genome remains associated with the human genome in stable proportions, thus without showing indication of mobilization or bystander transduction of mouse cells.

In parallel, another PCR able to discriminate whether LV DNA integrated in mouse genome was set up, in order to exclude that a mobilization from human to mouse cells had occurred. This PCR amplifies vector DNA integrated in the proximity of mouse repetitive and highly interspersed B2 SINE family elements ([Follenzi et al. 2002](#)). As these sequences constitute approximately 0.7% of total mouse genomic DNA (estimates ranging from 2500 to 100000) and are only found at low abundance in humans (< 50), it is likely that most integrants in the mouse genome are found at a PCR-amplifiable short distance from one such element. The results of these studies have allowed to establish that bystander transduction does not occur above a threshold detection level in several tissues of the mice transplanted with transduced HSPC.

2.7.2. Germline transmission

Because the risk of inadvertent germ line transmission associated with the administration of *ex vivo* transduced human cells is considered “low” or “minimal” according to EMA and ICH, respectively, and animal testing of human cells may be difficult or not meaningful, non-clinical germ line transmission studies of human genetically modified cells are not recommended (EMA Guideline on non-clinical testing for inadvertent germline transmission of gene transfer vectors, EMA/273974/2005 and CHMP/ICH/469991/2006).

Moreover, no evidence of germ line transmission nor of transgene expression in germ cells after *in vivo* delivery of RV and LV into experimental animals have been reported to date. In a study of testicular tubule injection of LV in mice, the sperm collected from recipient testes were able to generate normal pups and none of the offspring carried the transgene ([Ikawa et al. 2002](#)). Rat spermatogonial stem cells, however, can be effectively transduced *ex vivo* by LV and generate viable transgenic offspring upon re-implantation into rat testes. Moreover, LV can transduce *in vitro* fertilized eggs from a variety of species, including mouse, rat and pig. Indeed, LV are becoming common tools for the generation of transgenic animals by *in vitro* oocyte transduction followed by *in utero* implant ([Park 2007](#)).

Thus, given the concerns for residual infectious vector associated with the transduced HSPC, we have expanded the biodistribution study of vector and HSPC progeny in *Rag2*-, *Il2r-gamma*

chain-/- mice described above to test for the presence of LV genome in the gonads at the time of sacrifice, 2 months post-transplant. For this experiment, we extracted DNA from the gonads and performed: 1) qPCR for vector and human genome content, as described above; 2) nested B2-specific PCR for vector integrated within the mouse genome, as described above. The assays are designed in a way that if any vector DNA is detected in the gonads it should be associated with the human genome, and in corresponding ratio as observed for the other organs of the mouse. Our results show no detectable vector in the gonads of those mice by qPCR, which was also confirmed by nested B2-specific PCR.

Last but not least, we should remind that the concerns for germ line transmission of the genetic modification are unfortunately further mitigated by the severe disability and short life expectancy of the patients to be enrolled in the trial, and by the administration of conditioning regimen which is often associated to the induction of sterility.

2.7.3. Genotoxicity and carcinogenicity

Insertional oncogenesis is a possible consequence of vector integration into the human genome. Several decades of studies of gamma- or onco-retrovirus induced lymphomas/leukemias ([Lund et al. 2002](#); [Suzuki et al. 2002](#); [Uren et al. 2005](#)) in mice have shown that proviral insertions near or within proto-oncogenes can trigger their over-expression and/or aberrant transcription and lead to cell transformation. Both mechanisms of oncogene activation are dependent on the strong transcriptional enhancer/promoter elements contained in the viral Long Terminal Repeat (LTR) ([Uren, Kool et al. 2005](#)). Initially, the gamma retrovirus-derived vectors (gRV) proposed for gene therapy applications were considered to pose a much lower risk of insertional mutagenesis compared to gamma-retrovirus infection, given the lack of replication and the limited number of integrations occurring during the *ex vivo* transduction procedure. Unfortunately, however, gRV-induced activation of the *LMO2* oncogene and/or other oncogenes resulting in leukemogenesis has now been reported in 5 out of 20 X-linked SCID patients treated with HSPC gene therapy ([Hacein-Bey-Abina et al. 2003](#); [Pike-Overzet et al. 2007](#)). Similarly, clonal expansions resulting in myelodysplastic syndrome were ascribed to gRV insertion into the *EVII*, *PRDM16* or *SETBP1* ([Ott et al. 2006](#); [Ott et al. 2007](#)) proto-oncogenes in 3 CGD patients treated with HSPC gene therapy.

In light of these serious adverse events, the oncogenic risk of vector integration in HSPC had to be re-evaluated ([Baum and Fehse 2003](#); [von Kalle et al. 2004](#)) and a great effort went into defining the integration pattern of the different vectors and its impact on endogenous gene transcription ([Schroder, Shinn et al. 2002](#); [Wu, Li et al. 2003](#); [Hematti et al. 2004](#); [Lewinski et al. 2006](#)). A better understanding of the risk associated with gRV and LV in HSPC gene therapy is emerging from a growing number of pre-clinical studies which have modeled genotoxicity in *in vitro* cell immortalization assays and in *in vivo* murine models of leukemia/lymphoma development ([Williams 2006](#); [Will et al. 2007](#)) and from transcriptional studies of gene de-regulation at the vector integration sites in cells transduced *in vitro* or retrieved from transplanted mice and patients ([Recchia et al. 2006](#); [Ryu et al. 2008](#)).

Direct comparison of gRV and LV in these assays demonstrates that prototypical LV have a substantially lower oncogenic potential than gRV ([Montini et al. 2006](#); [Modlich et al. 2008](#)). Important features contributing to the lower genotoxicity of LV as compared to conventional gRV are likely to be: 1) the self-inactivating design, which prevents LTR-dependent effects on

the transcription of genes neighboring the integration site; 2) the use of a vector internal promoter to drive transcription of the therapeutic transgene, which is chosen among those with moderate transcriptional activity as compared to gRV LTR (these aspects are discussed in more details in paragraph 6.4.).

Moreover, it has been demonstrated that both gRV and LV display a non random genomic distribution pattern, which is characteristic for each vector and that may thus influence the safety profile of each vector differently. Indeed, both gRV and LV integrate more frequently within genes than expected of random insertion throughout the genome, gRV preferentially integrate near the promoters and CpG islands of actively transcribed genes ([Wu et al. 2003](#), [Bushman et al. 2005](#)). This preference makes it more likely for the LTR to interfere with regulation of the genes near the integration site ([Schroder et al. 2002](#); [Wu, Li et al. 2003](#); [Bushman, Lewinski et al. 2005](#); [De Palma et al. 2005](#)). Furthermore, when hot spots of vector integration were identified in the mouse and human HSPC genome, striking differences were observed between gRV and LV ([Montini, Cesana et al. 2006](#); [Aiuti et al. 2007](#); [Bushman 2007](#); [Cattoglio et al. 2007](#); [Deichmann et al. 2007](#); [Schwarzwaelder et al. 2007](#)). gRV, but not LV, integrations occurred at proto-oncogenes and genes involved in the control of cell proliferation with a frequency significantly higher with respect to the expected random frequency. LV integrations appeared to occur more broadly across gene classes and hot spots were found at low frequency and in locations characterized by high density of expressed genes.

Indeed, the unique propensity of gRV to integrate near potentially dangerous genes may be an important factor determining genotoxicity, and the lack of such preference in the case of LV may well contribute to the improved safety profile demonstrated in preclinical gene therapy models.

Beside the intrinsic features of the vector, however, other factors may contribute significantly to the risk of oncogenesis in gene therapy treated patients ([Woods et al. 2006](#)), including disease-related conditions that may increase the susceptibility to develop tumors (such as the accumulation of immature progenitors or immune deficiency) and the biological activity of the therapeutic transgene itself.

In order to detect possible genotoxic effect of the WASP LV, a recently developed assay was performed by Génethon. This test detects the presence of clonal dominance of insertional mutants which expand in initially polyclonal cultures of primary murine hematopoietic cells within two weeks after gene transfer and acquire serial replating ability, the extent of which provides a measure of clonal fitness ([Modlich et al. 2006](#)). The test has some limitations, since it detects essentially only genotoxicity related to EVI1 insertions and is based on a mouse *in vitro* transformation after *in vitro* cytokine expansion. In none of the three assays conducted with WASP LV, induction of replating activity was observed. As expected, a positive control represented by gRV containing a strong myeloid viral promoter (SFFV) showed a high replating activity. Thus, the WAS vector did not exhibit any genotoxic potential, confirming its safety also in this context.

To efficiently analyze high numbers of lentiviral insertion sites in the DNA of transduced cells, Génethon has developed an improved high-throughput method called vector integration tag analysis (VITA), described in ([Mantovani et al. 2006](#)). VITA is based on the identification of genomic tags associated to the insertion sites, which are used as signatures of the integration events. We analyzed the integration sites following WASP-encoding w1.6W LV transduction of murine WKO cells and compared the pattern of integration sites obtained in a population of

hematopoietic progenitor cells cultured *in vitro* with that of cells capable of engraftment *in vivo* ([Mantovani et al., 2009](#)). Lineage-negative hematopoietic progenitor cells were prepared from WKO mice and were transduced *ex vivo* with the w1.6W LV and transplanted into lethally irradiated WKO mice. Extracts from the Lin- cells (pre-infusion), as well as blood and BM of mice after gene therapy were used to prepare genomic DNA and were compared by VITA technique to analyze the vector insertion sites.

A high number of unique junctions was found in the cultured cells (more than 90 unique junctions in a first approach without concatenation, more than 300 in a second approach with concatenation). In blood and BM samples, the numbers of unique junctions were significantly lower with respectively 17 to 28 unique sites in blood samples and 8 to 13 unique sites in BM samples, depending on the animal analyzed. In contrast to what observed with the cultured cell sample, the number of unique sites found in the blood/BM samples reached a plateau as number of sequences increased (80-120 junctions sequenced for each point). As previously reported by others, we found a bias toward insertion of the vector into genes, but no obvious bias for the distribution of insertions into specific categories of genes. No common integration sites between the *in vitro* and *in vivo* samples and no evidence of integrations shared by different mice were detected.

Altogether, the analysis of the w1.6W LV integration sites in murine cells revealed insertions into a polyclonal population, no hotspot and no insertion of the vector into previously identified CIS.

2.7.3.1. Integration analyses in other trials

LV-based HSPC gene therapy was recently tested in ALD patients. The vector tested was a third-generation LV similar to the one proposed for this trial, except for the internal promoter driving the therapeutic cDNA, which was derived from the strong MND LTR. A clear clinical benefit has been reported in the two treated patients together with stable polyclonal hematopoietic repopulation by the transduced HSPC and no evidence for skewing in genomic distribution or specific gene classes by comparing vector integration sites in pre- and post-transplant samples ([Cartier N. et al., 2009](#)). These data provide compelling evidence that LV provide for efficient, safe and long-term marking of human hematopoiesis as predicted by a large amount of pre-clinical studies.

In another recent trial of LV-based HSC gene therapy for beta-thalassemia, a self-limiting expansion of a clone bearing a LV insertion putatively leading to a gain-of-function in growth control was recently reported in a beta-thalassemia patient ([Cavazzana-Calvo M. et al. Nature 2010](#)). Further investigations are needed to clarify the potential contribution of this insertion to the observed clonal expansion and its benign or pre-malignant nature. Moreover, several additional factors may have contributed to the findings in the thalassemia trial, including a complex vector design and the use of non-purified low titer vector that resulted in the transplantation of very few transduced HSPC and a long-delayed *in vivo* marking rate.

In summary, our studies and recent preliminary findings from clinical trials indicate that integration of prototypical SIN LV has low genotoxic potential and, together with the high gene transfer efficiency and the therapeutic efficacy demonstrated in pre-clinical models, provide a major scientific rationale for advancing WAS LV to clinical experimentation.

2.7.4. Immunogenicity

Even though immunogenicity is considered in international guidelines for GTMPs, it is unlikely that the proposed therapeutic approach may elicit an immune response either against the therapeutic gene product or against the viral vector.

The infusion of genetically modified cells occurs, in the proposed clinical protocol, following the administration of a non-myeloablative conditioning regimen known to establish a certain degree of tolerance to donor encoded antigens in the context of allogeneic transplant.

Further, the drug product consists of CD34+ genetically modified cells exposed to the viral vector *ex-vivo*. It is recognized that this procedure has a lower anti-vector immunogenic risk when compared to *in vivo* administration of viral vectors. In addition, WASP is an intracellular protein, its expression in the vector is regulated by the endogenous, physiological promoter, and WAS protein levels are regulated by the WIP molecule.

For these reasons, no *in vivo* pre-clinical studies for immunogenicity have been performed. Moreover, there was no evidence of immune mediated elimination of WASP transduced cells in the murine model of gene therapy, since transduced cells persisted long term with evidence of selective advantage.

Nonetheless, a careful assessment of any immune response will be performed by monitoring anti-WASP and anti-HIV proteins (anti-p24) antibodies every 6 months for the first year, then once a year during the clinical trial follow up period.

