4.2.2. Secondary safety endpoints

a) *Lack of immune response to transgene*

The lack of immune response towards the transgene will be measured by antibodies to WASP (immunoblot analyses).

b) Overall safety surveillance

This will be evaluated on the basis of clinical and laboratory parameters recorded and monitored during the follow up of the treated patients, according to the assessment plan. A descriptive analysis will be performed on AE, AR, SAE/SAR, UAR, SUSAR, and events will be classified for frequency, severity and body system involved.

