6.11. Supportive therapy

- During hospitalization, patients will be cared for in an isolation unit.
- Beginning before conditioning until recovery from severe neutropenia (ANC<500/ μ l) or discharge: oral decontamination and mouth care according to local standards.
- Pentamidine (nebulized) as first line *Pneumocystis jirovecii* prophylaxis from day -30 until complete immunological reconstitution.
- Antibacterial and antifungal prophylaxis according to local standards.

- Acyclovir as Herpes Simplex-prophylaxis until complete immunological reconstitution.
- Intravenous substitution to maintain immunoglobulin IgG >5g/l.
- Hydration of 3L/m² will be given during the conditioning phase (from day -4 to 24 hours after Busulfan).
- CMV (PCR), EBV (PCR) and adenovirus (PCR) viral load will be determined weekly till day +90. If repeatedly negative, after day +90, the interval of testing could be prolonged. Pre-emptive therapy with Ganciclovir or Foscarnet will be administered, according to local standards, if CMV positive.
- Pre-emptive therapy with Rituximab will be administered to EBV-positive patients after gene therapy in case of repeated increase of EBV viral load, according to local standards.
- Erythrocyte and thrombocyte concentrates will be substituted according to local standard. The decision to administer erythrocytes or platelets transfusions should incorporate individual clinical characteristics of the patients and not simply be a reflexive reaction to the platelet count. All blood products will be leukocyte depleted and irradiated.
- The need for a platelet infusion will be evaluated by the Investigators based on several factors, including:
 - platelets <20 x 10⁹/L;
 - the presence of active bleeding;
 - stability of thrombocytopenia;
 - concurrent infection and febrile condition;
 - immune thrombocytopenic purpura;
 - use and response to thrombopoietin (TPO) receptor agonists;
 - presence of risk factors for bleeding (such as an upcoming invasive surgical procedure);
 - toxicity which may lead to an increased risk of bleeding;
 - subjects at risk of fall and trauma; and
 - overall clinical condition of the subject.
- Several factors are considered in deciding whether the interruption of IVIG can be stopped:
 - stable trough levels of IgG (immunoglobulin G) remaining at or above 5 g/L;
 - absence of symptoms of infections or positivity at laboratory tests for pathogens;
 - the presence of adequate levels of B cells in the peripheral blood;

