8.4.3. Immune response to transgene

Patients will be monitored for antibodies anti-WASP for the lack of immune response to transgene every 6 months for the first year, then at year 2 and year 3. Moreover, anti-HIV antibodies (anti-p24) will be monitored at the same time points.

Table 10 Safety follow up (from 0 to 3 years)

Parameter			Immune response to transgene
Time point	RCL	ACP	
Baseline	X	X	X
+ 30 days	X		
+ 90 days	X		
+ 180 days	X	X	X
+ 1 y	X	X	X
+ 1,5 y		X	
+ 2 y	X	X	X
+ 2,5 y		X	
+ 3 y	Archive	X	X

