Response to vaccination will only be looked at in subjects who have completed the required schedule for the specific vaccination and have had a period of at least 90 days after their last IVIG infusion.

Reference values to define protective or positive responses are summarised below for each specific antigen.

Table 6 Reference values for protective response by antigen

Parameter	Protective response cut-off	Unit
Tetanus Toxoid	820	cpm
Tetanus IgG	0.4	IU/mL
Pneumococcus IgG	200	titre
Pneumococcus IgM	100	titre
Pertussis IgG Antibody	11	Arbitrary U
Hepatitis B Virus Surface Antibody	100	mU/mL
Hemophilus influenzae B Antibody	1	mg/L
Diphtheria IgG Antibody	0.4	IU/mL

A summary of response at any point within the first 3 years after GT as well as over the whole follow-up phase will be produced. In addition, the longitudinal profiles over time of responses to vaccinations will be described together with vaccinations in a listing.

A summary of the number of IVIG infusions per treatment phase will be presented along with the rate of infusions per year of observation.

A summary of time to sustained IVIG discontinuation will be produced for subjects who no longer need IVIG infusions. The cessation of sustained IVIG treatment is defined as a period of 3 months post gene therapy without IVIG treatment. The time to discontinuation will be presented in a table and Kaplan Meier plot including median time to discontinuation and 95% confidence interval.

Separate listings will be produced for patients requiring IVIG infusions and time to IVIG discontinuation (for those subjects who no longer need IVIG infusions).

9.1.6 Platelet counts and Mean Platelet Volume.

Absolute values of platelet count and mean platelet volume (MPV) as well as change from baseline will be calculated according to the planned follow up visits and including platelet count collected for clinical reasons during follow up (in infusion independent subjects). Baseline platelet count will be calculated as the median of the (at least three) determinations performed before beginning of treatment.

Normalization of MPV is defined as MPV within the normal range (MPV \geq 7.4 fL for children (< 18 years) and MPV \geq 9.1 fL for adults). Platelet count data obtained within 7 days following platelet infusions will not be considered for evaluation.

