10.2.1 Immune Response to Transgene

The lack of immune response towards the transgene will be measured by antibodies to WASP.

A summary table detailing the number and percentage of subjects with present anti-WASP antibodies will be generated with 95% CI of the percentage calculation. The longitudinal profile over time of anti-WASP antibodies will be described with a listing.

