10.2.3 Clinical Laboratory Evaluations

Clinically relevant abnormal values will be recorded in the Concomitant Disease page or Adverse Events page. Clinical laboratory evaluations will be summarised with descriptive statistics by visit. Any haematology or clinical chemistry test results which are outside the normal ranges will be flagged as high or low relative to the normal range.

The normal range of laboratory test parameters will also be provided in an additional listing as a reference.

Box plots will be generated to provide a graphical overview of the following laboratory parameters over time.

Table 12 Laboratory parameters where box plots will be generated

Chemistry	Haematology	Liver Function Tests (LFTs)
Creatinine	Platelet Count	Aspartate aminotransferase (AST)
	Haemoglobin	Alkaline Phosphatase (ALP)
	Haematocrit	Alanine aminotransferase (ALT)
	White Blood Cell Count (Leukocytes)	Total Bilirubin

In addition to all available data, the box plots will include the maximum post-baseline value for each subject. All data will be presented relative to the upper limit of normal (ULN). In addition, for the haematology parameters only, box plots will also be produced showing the data relative to the lower limit of normal (LLN), including the minimum post-baseline value for each subject. For liver function tests only, a horizontal line will be included in the figures denoting 2xULN.

Individual profiles of LFT, relative to the ULN, over time will be plotted.

Tables will also be created for shifts in parameters with reference to the reference range. Results will be summarised per parameter per visit. Shifts compared to the reference range (low, normal, high) from baseline to minimum value and maximum value post-baseline will be presented for laboratory parameters. Listings of laboratory data outside the normal range and a listing of all laboratory data will be created.

Summary statistics of immunoglobulins (IgA, IgG, IgM, IgE) will be presented over time. IgG evaluations taken within 3 months of IVIG administration will be excluded from the summary.

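### Anti-WASP antibody testing has two conflicting schedules, one yearly through follow-up and one ending at year 3, and the SAP counts any antibody present as a response to the transgene without using the baseline sample.

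*Protocol*

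**What the plan says.** **Endpoint.** Protocol 4.2.2 makes lack of immune response to the transgene a secondary safety endpoint: "The lack of immune response towards the transgene will be measured by antibodies to WASP (immunoblot analyses". Section 8.3.2 also includes it in the long-term safety of the infused cells.

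**Schedule.**
- Protocol 2.7.4: anti-WASP and anti-p24 "antibodies every 6 months for the first year, then once a year during the clinical trial follow up period".
- Protocol 8.4.3: anti-WASP "every 6 months for the first year, then at year 2 and year 3", with anti-p24 at the same time points.
- "Table 10 Safety follow up (from 0 to 3 years": marks baseline, 180 days and years 1, 2 and 3.
- Table 8b (years 4 to 8): no column for this test.
- Protocol 4.1.2: the Follow Up phase consists of an initial period of at least 3 years and a long-term period from 3 up to 8 years. Transfer to the separate long-term study is possible after at least 5 years.

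**Analysis.** SAP 10.2.1: "A summary table detailing the number and percentage of subjects with present anti-WASP antibodies will be generated", with a 95% CI and a listing over time. SAP Table 11 marks this parameter for absolute displays only, not change from baseline. The output is Table 14.3.2.1.1, on the Mobilisation Set, and its title presents the patients counted as having a positive immune response to the transgene.

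**IVIG and B cells.** Rituximab is planned on day -22. IVIG is given to keep IgG above 5 g/L, and one factor in stopping it is "the presence of adequate levels of B cells in the peripheral blood". For vaccine responses, SAP 9.1.5 uses only patients who "have had a period of at least 90 days after their last IVIG infusion". For immunoglobulins, SAP 10.2.3 states: "IgG evaluations taken within 3 months of IVIG administration will be excluded from the summary". SAP 10.2.1 has no corresponding rule.

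**The concern.** There are three problems, of unequal weight.

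1. Two sections of the same protocol give different end points for the same safety test. A site that follows 8.4.3 will not produce the data that 2.7.4 promises, and the final report cannot meet both.
2. The table counts antibody presence but is labelled as a response to the transgene. A response implies a change after exposure. The sample needed to show that change is scheduled, but the counting rule does not use it.
3. The SAP treats recent IVIG as a reason to restrict two other antibody outputs and says nothing about it for anti-WASP. Nor does it say whether the percentage is by visit or ever-positive.

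At stake is a named safety endpoint reported as a percentage of a very small group, where reclassifying one patient visibly changes the result.

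**Working it through.** The plan states no precision or error figure for this endpoint, so there is nothing to reproduce.

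**Step 1: count the post-treatment tests per patient.**

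| Source | Time points | Tests |
|---|---|---|
| 8.4.3 and Table 10 | 0.5, 1, 2, 3 years | 4 |
| 2.7.4, to the 5-year minimum | 0.5, 1, 2, 3, 4, 5 years | 6 |
| 2.7.4, to year 8 | 0.5 year, then years 1 to 8 | 9 |

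The gap is 6 − 4 = 2 to 9 − 4 = 5 tests per patient, all after year 3. For 8 treated patients this is 8 × 2 = 16 to 8 × 5 = 40 anti-WASP assays.

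**Step 2: apply the SAP counting rule to each possible pattern.**

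| Baseline | Afterwards | Counted under SAP 10.2.1 | New response shown? |
|---|---|---|---|
| Absent | Absent | No | No |
| Absent | Present | Yes | Yes |
| Present | Present | Yes | No |
| Present | Absent | Depends on by-visit or ever-positive, and on whether baseline is included | No |

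The third pattern is misclassified under either form of the percentage. The fourth cannot be resolved from the text.

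**Step 3: size of one misclassified patient.** Assume a denominator of 8, the planned number treated; the Mobilisation Set size is not given. One case adds 1/8 = 12.5 percentage points. Protocol 12.5 specifies Wilson intervals for proportions:

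(p + z²/2n ± z·√[p(1−p)/n + z²/4n²]) / (1 + z²/n), with z² = 3.8415.

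- 0/8: the upper limit reduces to z²/(n + z²) = 3.8415/11.8415 = 32.4%.
- 1/8: centre (0.1250 + 0.2401)/1.4802 = 0.2467; half-width 1.96 × √(0.01367 + 0.01501)/1.4802 = 0.2242; interval 2.2% to 47.1%.

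**Step 4: IVIG and B cells.** The documents give no IVIG stop date and no B-cell recovery time. The one relevant marker is that vaccine responses, assessed off IVIG, are foreseen more than 1 year after gene therapy (Protocol 4.3.1). On that timeline, 2 of the 4 tests in 8.4.3 (6 months, 1 year) fall at or before the marker and 2 (years 2 and 3) after it. Without dates, the true number could be anywhere from 0 to 4.

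The two influences act in opposite directions. B-cell depletion could hide a response, whereas donor immunoglobulin could at most add reactivity.

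For illustration only, with no positives and an assumed number of unaffected patients, the upper limit z²/(n + z²) is:
- n = 6: 3.8415/9.8415 = 39.0%
- n = 4: 3.8415/7.8415 = 49.0%
- n = 2: 3.8415/5.8415 = 65.8%

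**The case against.** **The schedule conflict may be only apparent.** Section 2.7.4 is background, 8.4.3 and Table 10 are the operative plan and agree with each other, and the follow up period could mean the initial 3 years. That reading is possible, but 2.7.4 does not say so, and the protocol defines its Follow Up phase to year 8. It is also true that loss of corrected cells, the consequence 2.7.4 discusses, remains monitored to year 8 through vector copy number and WASP expression. This lowers the stakes but leaves the conflict.

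**The listing shows everything.** With about eight patients, a reader can find each baseline and later result in the anti-WASP listing, and all intervals are nominal. This is fair, but the summary table would still carry a label that its counting rule does not support.

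**A stronger reading.** A reader might infer that absence of an immune response is judged mainly when antibody cannot be interpreted. The documents do not support this. They give no IVIG duration or B-cell recovery time, half of the tests in 8.4.3 fall after the point at which vaccine assessment off IVIG is foreseen, and the Baseline phase ends before rituximab. No passage says donor immunoglobulin carries anti-WASP, and IVIG alone would not produce a false negative.

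**Excluding results near IVIG.** Extending the 90-day rule to anti-WASP as an exclusion is also tempting. It would remove positive results from a table meant to detect them, so flagging is preferable.

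**Conclusion.** Two findings stand on the text. The anti-WASP and anti-p24 schedules conflict: 4 post-treatment tests per patient against 6 or 9, depending on when the patient transfers. The SAP's counting rule would also label pre-existing antibody as a response to the transgene. One such patient adds 12.5 points and moves the Wilson upper limit from 32.4% to 47.1%, assuming a denominator of 8. Whether any patient has antibody at baseline is unknown.

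The missing IVIG and B-cell flag is an inconsistency with the SAP's own handling of other antibody outputs. Its effect cannot be determined from the documents, and that all results are counted is inferred from the SAP's silence. It justifies a flag and a supportive display, not a claim that the endpoint is uninterpretable.

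**What to change.** **SAP 10.2.1 and Table 14.3.2.1.1**
- Define an immune response as anti-WASP antibody absent at baseline and present at a later visit.
- Report baseline-positive patients on a separate line.
- State whether the percentage is by visit or ever-positive.
- Keep all results in the main table. Flag each by time since last IVIG and by CD19+ count, which is already collected. Show the number of unaffected patients and the corresponding Wilson interval alongside as a supportive display. Do not drop positives.

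**Protocol**
- Reconcile 2.7.4 with 8.4.3, Table 10 and Table 8b, for both anti-WASP and anti-p24.
- If yearly testing is intended, serum archived under section 7.2 and Table 8b could be used from year 4 onward.

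**Cost.** The SAP change is wording plus flags built from data already collected, and the baseline sample is already scheduled. Yearly testing, if intended, means about 16 to 40 anti-WASP immunoblots for 8 patients, with anti-p24 assays in addition. The supportive display will have smaller denominators and wider intervals.
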